9.2. Analysis of the Secondary Effectiveness Endpoints

Endpoints have been classified relative to their distribution (binary, multinomial, or continuous), and the number of times the variable was recorded.

Binary Variable Assessed at a Single Time Point (3 endpoints):

- **Secondary Endpoint:** Procedure success: defined as successful treatment of at least 6 cm of duodenum segment.
- **Secondary Endpoint:** Proportion of treated patients with an HbA1c improvement of $\geq 0.5\%$ from baseline at 24 weeks (24 week score minus baseline score).
- **Secondary Endpoint:** Proportion of treated patients with an HbA1c improvement of $\geq 0.5\%$ from baseline at 24 weeks maintained at 48 weeks.

For each set of results for each Comparison Set, the following 2 research questions will be addressed. Results will be presented using the Level 1 tables b through e.

For the endpoints measured on a binary scale, what are the overall estimates in the FAS population.

For the endpoints measured on a binary scale, is there a difference in the estimates in the FAS population based on the generation of the device, voltage, and single vs. double treatment?

Multinomial Variable Assessed at a Single Time Point (1 endpoint):

- **Secondary Endpoint:** Proportion of patients that have a change in glucose-lowering medication usage from baseline.

For each set of results for each Comparison Set, the following 2 research questions will be addressed. Results will be presented using the Level 1 tables b through e.

For this endpoint measured on a multinomial scale, what are the overall estimates in the FAS population.

For this endpoint measured on a multinomial scale, is there a difference in the estimates in the FAS population based on the generation of the device, voltage, and single vs. double treatment?

Continuous Variable Assessed at a Single Time Point (3 endpoints):

- **Secondary Endpoint:** Procedure time: defined as the time between the Endogenex catheter insertion and the catheter removal.
- **Secondary Endpoint:** Change in liver enzyme from baseline at 24 weeks [Alanine Aminotransferase (ALT)].
- **Secondary Endpoint:** Change in liver enzyme from baseline at 24 weeks [Aspartate Aminotransferase (AST)].

For each set of results for each Comparison Set, the following 2 research questions will be addressed. Results will be presented using the Level 1 tables b through e.

For each endpoint measured on a continuous scale, what are the overall estimates in the FAS population.

For each endpoint measured on a continuous scale, is there a difference in the estimates in the FAS population based on the generation of the device, voltage, and single vs. double treatment?

Continuous Variable Assessed at Multiple Time Points (11 endpoints):

- **Secondary Endpoint:** Change from baseline (post-baseline minus baseline) in HbA1c reported for each pre-specified study visit.
- **Secondary Endpoint:** Change from baseline (post-baseline minus baseline) in Fasting plasma glucose (FPG) reported for each pre-specified study visit.
- **Secondary Endpoint:** Change from baseline (post-baseline minus baseline) in Insulin-resistance by HOMA-IR reported for each pre-specified study visit.
- **Secondary Endpoint 6a:** Change from baseline (post-baseline minus baseline) in Post-prandial plasma glucose (PPG) reported for each pre-specified study visit.
- **Secondary Endpoint 6b:** Change from baseline (post-baseline minus baseline) in beta cell function reported for each pre-specified study visit.
- **Secondary Endpoint 6c:** Change from baseline (post-baseline minus baseline) in disposition index reported for each pre-specified study visit.
- **Secondary Endpoint:** Change from baseline in blood pressure by visit.
- **Secondary Endpoint:** Change in lipid profile from baseline by visit: total cholesterol
- **Secondary Endpoint:** Change in lipid profile from baseline by visit: triglycerides

- **Secondary Endpoint:** Change in lipid profile from baseline by visit: HDL
- **Secondary Endpoint:** Change in lipid profile from baseline by visit: LDL
- **Secondary Endpoint:** Change in weight from baseline (post-baseline minus baseline) by visit. Weight will be evaluated based on the intra-patient percent change from baseline. (% TBWL: % Total Body Weight Loss)
- **Secondary Endpoint:** Time in Range (TIR) based on Continuous Glucose Monitoring (CGM) by visit

For each set of results for each Comparison Set, the following 2 research questions will be addressed. Results will be presented using the Level 3 tables b through e.

For each endpoints measured on a continuous scale, what are the overall estimates in the FAS population assessed over time.

For each endpoint measured on a continuous scale, is there a difference in the estimates in the FAS population based on the generation of the device, voltage, and single vs. double treatment assessed over time?

The list of the top-line tables to be generated are presented below:

Table 14.4.1 entitled *Overall Summary of Procedure Success and Procedure Time (FAS Population)*

Table 14.4.2 entitled *Overall Summary of HbA1C, Fasting plasma glucose (FPG), Insulin-resistance by HOMA-IR, and Post-prandial plasma glucose (PPG) by Visit (FAS Population)*

Table 14.4.3 entitled *Overall Summary of Beta Cell Function by Visit (FAS Population)*

Table 14.4.4 entitled *Overall Summary of HbA1c improvement ≥ 0.3 points by Visit (FAS Population)*

Table 14.4.5 entitled *Overall Summary of Percent Change in Body Weight by Visit (FAS Population)*

Table 14.4.6 entitled *Overall Summary of Glucose-Lowering Medications by Visit (FAS Population)*

Table 14.4.7 entitled *Overall Summary of Liver Enzymes and Lipids by Visit (FAS Population)*

Table 14.4.8 entitled *Overall Summary of Blood Pressure Measurements by Visit (FAS Population)*

Table 14.4.9 entitled *Overall Summary of Continuous Glucose Monitoring (CGM) by Visit (FAS Population)*

10. SAFETY

The following sections describe how the safety results will be analyzed and reported. The safety analyses will be conducted using the ITT population, defined as all patients in whom the endoscopic screening procedure was initiated. In addition to the reporting of adverse events, Safety will include an examination of hypoglycemia, pancreatic enzymes, and endoscopic follow-up.

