5.3 Point of Enrollment

The point of enrollment occurs when a participant has provided written informed consent and an energy delivery has been attempted during the index procedure.

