11.3 Analysis Populations

The following analysis populations are defined for the study: Intent-to-Treat (ITT), modified Intent-to-Treat (mITT), Per-Protocol (PP) and Completed Cases (CC). The primary safety analysis will be performed on the ITT population. The primary effectiveness analysis will be performed on mITT population.

- Intent-to-Treat: The Intent-to-Treat population includes all enrolled participants as defined in Section 5.3 regardless of whether or not the participant received the full treatment.
- Modified Intent-to-Treat: The mITT population consists of the ITT population participants who received the target treatment (at least 6 cm of duodenum treatment) and that have at least one post-treatment follow-up.
- Per-Protocol: The Per-Protocol population is a subset of the mITT population and includes all participants who received the target treatment, do not have any major eligibility violations, and maintained stable glucose-lowering medications for 24 weeks post procedure.

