11.4.2 Primary Endpoint Analysis

The primary endpoint of the study is proportion of participants experiencing one or more device- or procedure-related serious adverse events within 12 weeks post procedure. The analysis will be performed using the ITT population. No hypothesis will be tested as the analytical intent is to characterize outcomes.

Additionally, an overall summary of AEs will be provided including the number of events and percent of participants with any AEs, SAEs, and UADEs. For each type of event, the number of events and number and percent of participants with the event will be provided. Separate summaries of all adverse events will be summarized by relationship to device and procedure.

Only events occurred at or after the index procedure will be counted for the purpose of safety analysis. Events occurred prior to the index procedure will be considered as medical history.

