3. INTRODUCTION

This statistical analysis plan (SAP) describes the planned statistical methods to be used during the reporting and analysis of data collected under the Clinical Investigation Protocol entitled *Safety and Feasibility of Endoscopic Application of a Novel Therapy for Duodenal Mucosal Regeneration in the Treatment of Type II Diabetes (REGENT-1-US Study)*, Doc. No. 346. This SAP should be read in conjunction with the study protocol and case report forms (CRFs).

The REGENT-1-US study is a multicenter, open-label, treatment-only study conducted in Australia. The study is designed to assess the feasibility and preliminary safety of the Endogenex device for endoscopic duodenal cellular regeneration in patients with type 2 diabetes (T2D) inadequately controlled on glucose-lowering medications. The protocol enrolled patients who were treated with non-insulin glucose-lowering agents; a tabulation of the treatment and number of patients is presented below.

Device Generation 1 / 600 Volts / Single Treatment (n)	Device Generation 1 / 600 Volts / Double Treatment (n)	Device Generation 2 / 750 Volts / Double Treatment (n)	All Patients (n)
3	7	10	20

This plan is developed for analysis and reporting of the 48-week follow up data. The SAP may be revised in the future to address additional follow up data analysis beyond 48 weeks, if necessary.

Patients are considered enrolled in the study once the patient has passed endoscopic screening and proceeded to the Index procedure. **Screen failures** are defined as patients who consented to participate in the clinical study and started the screening tests specified by the protocol but are not subsequently enrolled into the study. Procedure success was defined as at least 6cm of duodenum was successfully treated.

The following analysis populations are defined for the presentation of the results from this study: *Intent-to-Treat* (ITT), *Full Analysis Set* (FAS) [referred to in the study protocol as the modified Intent-to-Treat (mITT) population], *Per-Protocol* (PP) and *Completed Cases* (CC). (Ref. Section 11.3 of the study protocol).

The primary and secondary safety analyses will be performed using the ITT population. The primary effectiveness analyses will be performed using the FAS population. The Per-Protocol population and Completed-Cases population will be used for the sensitivity analyses of the primary and secondary effectiveness endpoints.

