Intent-to-Treat: The Intent-to-Treat population includes all enrolled patients, regardless of the patient having received the target treatment (at least 6cm of duodenum treated). The point of enrollment occurs when a patient has provided written informed consent and an energy delivery has been attempted during the index procedure.

Full Analysis Set: The FAS population consists of the ITT population patients who received the target treatment (at least 6 cm of duodenum treatment) and that have at least one post-treatment follow-up examination.

Per-Protocol: The Per-Protocol population is a subset of the FAS population and includes all patients who received the target treatment, do not have any major eligibility violations, and maintained stable glucose-lowering medications for 24 weeks post-procedure. The definition of what constitutes a major eligibility violations will be established before the study database is locked.

Completed Cases: The Completed Cases population is a subset of the Per-Protocol population and includes all patients who received the target treatment, do not have any major eligibility violations, and maintained stable glucose-lowering medications for 24 weeks post-procedure, and completed the final Week 48 End of Study Visit.

The details contained in this plan include the source code for the assessment of poolability across a myriad of factors and the analysis of each of the endpoints. Additionally, the structure of the table designs and a comprehensive index of the tables and listings has been provided.

This document contains information to support the generation of a Clinical Study Report (CSR). The planned analyses identified in this SAP may be included in regulatory submissions, medical presentations, and manuscripts. Exploratory analyses, not identified in this SAP, may be performed to support the clinical development program. Any post-hoc or unplanned analyses that are performed, but not identified in this SAP, will be clearly identified in the final report of the results. The structure and content of this SAP are designed to meet the requirements identified by the FDA and the International Conference on Harmonization (ICH) Guidance on Statistical Principles for Clinical Trials.

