5. STUDY OVERVIEW

5.1. Study Design and Description of the Study Device

This is a multicenter, open-label, treatment-only study conducted in the United States. A total of 20 participants is planned for the study. The study will test two treatment parameters. The first 10 participants will be treated at a generator setting of 600 Volts/13 bursts/350 KHz (600V) and the second group of 10 participants at 750 Volts/8 bursts/350KHz (750V). In the 600V group, the first 5 participants will be enrolled/treated with the investigational device sequentially with at least 14 days observation time between each procedure. In the 750V group, the first participants will be enrolled/treated with the investigational device sequentially with at least 6 days observation time between each procedure.

Participants with T2D inadequately controlled on 2-3 non-insulin glucose-lowering medication(s) will be screened for study eligibility. Eligible participants who consent to participate in the study will maintain his/her background glucose-lowering medication(s) stable (no medication or dose change) for at least 12 weeks prior to baseline visit.

The index procedure will be performed under general anesthesia or deep sedation and within 21 days from the baseline visit. Participants will undergo endoscopic screening immediately prior to the DMR procedure, and eligible participants will undergo the DMR procedure. Participants may be discharged per local hospital's guideline; an overnight stay is not required but allowed per local policy and investigator's clinical judgement. A participant is enrolled in the study when the Endogenex catheter insertion is attempted. Participants excluded during endoscopic screening will be considered a screen failure and will be followed for four weeks after the procedure for safety.

Post index procedure, participants will be on a transitional diet consisting of clear liquids for 24 hours followed by a full liquid diet for 3 days, pureed food for 3 days, and soft food for one week, and then return to normal food as tolerated.

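### SAP section 10 defines the ITT population for safety as everyone who began endoscopic screening, contradicting the ITT definition in SAP sections 3 and 6 and leaving the safety denominator unsettled

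*SAP*

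**What the plan says.** SAP section 10 opens the safety analyses with its own definition of ITT: "The safety analyses will be conducted using the ITT population, defined as all patients in whom the endoscopic screening procedure was initiated".

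The paragraphs headed Intent-to-Treat in SAP sections 3 and 6 define ITT as the enrolled patients and fix enrollment as follows: "The point of enrollment occurs when a patient has provided written informed consent and an energy delivery has been attempted during the index procedure". Both sections assign the primary and secondary safety analyses to ITT.

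Other SAP sentences place enrollment elsewhere. The opening text of section 3 says: "Patients are considered enrolled in the study once the patient has passed endoscopic screening and proceeded to the Index procedure". Section 5.1 says: "A participant is enrolled in the study when the Endogenex catheter insertion is attempted". The first paragraph of section 6 needs only that endoscopic screening was passed.

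On patients who fail the endoscopy, section 5.1 says: "Participants excluded during endoscopic screening will be considered a screen failure and will be followed for four weeks after the procedure for safety". Sections 3 and 6 describe screen failures as consented patients who are never enrolled.

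The supplied Protocol 196 agrees with the labelled ITT paragraphs. Its section 5.3 says: "The point of enrollment occurs when a participant has provided written informed consent and an energy delivery has been attempted during the index procedure". Its section 11.3 says: "The primary safety analysis will be performed on the ITT population". However, the SAP names a different governing protocol, Doc. No. 346, which is not among the documents.

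**The concern.** One label, ITT, covers two different sets of people in one plan. A patient excluded at endoscopy is outside ITT under sections 3 and 6 and inside it under section 10. Sections 10.1.3 and 10.1.4 report the adverse event and serious adverse event tables on ITT, so a programmer who follows section 10 would put that patient in the denominator.

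The rest of the SAP has no place for such a patient. The study calendar, the partial-date rules for adverse events and the table columns all presuppose a study procedure. In a study of 20, a few additional patients visibly change a percentage and its confidence limits. If the choice is left open until the data are known, it can no longer be shown to have been made independently of them.

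**Working it through.** **1. The definitions side by side.** Three kinds of patient separate them.

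| Source | Rule | Fails endoscopic screening | Catheter insertion attempted, no energy attempt | Energy delivery attempted |
|---|---|---|---|---|
| SAP 10 | Screening endoscopy begun | In | In | In |
| SAP 6, first paragraph | Screening passed | Out | In | In |
| SAP 3, opening text | Screening passed, went on to index procedure | Out | In | In |
| SAP 5.1 | Catheter insertion attempted | Out | In | In |
| SAP 3 and 6, ITT paragraphs; Protocol 196, 5.3 and 11.3 | Consent and energy attempt | Out | Out | In |

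Section 10 is the only rule that admits screen failures. The remaining rules still disagree about a procedure abandoned between catheter insertion and energy delivery.

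**2. Following a screen failure through the SAP.**
- Section 7 sets Study Day 1 as the day of the DMR procedure. A screen failure has none, so the primary endpoint window in section 9, which ends at relative study day 84, cannot be placed.
- Section 10.1.2 fills several kinds of missing onset date with the procedure date. A screen failure has none.
- The Level 1 and Level 2 tables in section 7 have columns for device, voltage and treatment groups plus All Patients. A screen failure fits only the last.
- The model in section 9.1 uses the group as a classification effect. A patient without a group drops out, so the group comparison is unaffected.

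With *k* screen failures, the group columns still sum to 3 + 7 + 10 = 20 and All Patients becomes 20 + *k*.

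**3. Effect on a reported proportion.** Inputs: 20 patients from the table in SAP section 3, taken as all having had energy attempted; exact two-sided 95% limits, as sections 7 and 10.1.3 specify. The value of *k* is not in the documents; 0 to 5 is an assumption. The plan states no figure of its own to reproduce.

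For zero events in N patients, the upper limit is 1 − 0.025^(1/N):
- N = 20: 1 − 0.025^(1/20) = 16.8%
- N = 21: 16.1%
- N = 23: 14.8%
- N = 25: 1 − 0.025^(1/25) = 13.7%

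For one event, the upper limit is the 0.975 quantile of Beta(2, N − 1):
- 1/20 = 5.0%, interval 0.1% to 24.9%
- 1/25 = 4.0%, interval 0.1% to 20.4%

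The opposite direction, with no event in the 20 treated patients and one in a single screen failure:
- 0/20 = 0% (upper limit 16.8%) becomes 1/21 = 4.8% (upper limit 23.8%)

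At *k* = 0, with no procedure abandoned before energy delivery, all the definitions select the same patients.

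**The case against.** The best defence is that the practical reach is short. Section 10 introduces the tables that follow it. The primary endpoint sits in sections 9 and 9.1, which name ITT without redefining it, and sections 3 and 6 assign the safety analyses to ITT next to the energy-delivery definition. The section 3 table already puts All Patients at 20, screen failures are accounted for in the disposition table (section 8.1), and the group model would drop them. A broad safety set could also be deliberate, because the screening endoscopy carries risks of its own.

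Much of this stands. Only the All Patients column is exposed, and the effect on the primary endpoint is a possibility. What does not stand is the idea of a deliberate broader set: section 10 names no separate safety population and reuses the ITT label.

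Three stronger readings are tempting, and the documents do not support them.
- **That the primary denominator is enlarged.** Sections 9 and 9.1 can be read with the section 6 definition. The conflict leaves the denominator open; it does not settle it the wrong way.
- **That the wording makes the device look safer.** This needs event-free screen failures. Protocol 196, section 2.5.2, lists endoscopy and sedation complications among the anticipated events, and SAP section 10.1.3 counts events occurring during the study, so the rate could rise instead.
- **That unobserved person-time biases a result.** Screen failures are followed for four weeks against a 12-week endpoint, but section 7 bases adverse event reporting on patient counts. No planned output uses person-time.

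**Conclusion.** The contradiction is certain and can be shown from the SAP alone; Protocol 196 only corroborates it. Applied literally, section 10 gives adverse event tables whose total need not equal the sum of their columns and whose denominator includes patients the SAP itself calls not enrolled.

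The size is modest and conditional. At the assumed extreme of five event-free screen failures, the zero-event upper limit falls by 16.8 − 13.7 = 3.1 percentage points. The analysis is descriptive with no threshold, so no decision rule is affected. This should be corrected, but it does not undermine the study.

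Which enrollment point is correct cannot be settled here. Section 5.1, which carries design details absent from Protocol 196 (a United States setting and two voltage groups of 10), uses catheter insertion, so Doc. No. 346 may differ from the labelled ITT paragraphs.

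**What to change.** Before database lock:

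1. Confirm the enrollment point in Doc. No. 346.
2. Delete the endoscopic-screening clause from SAP section 10 and refer to the single ITT definition in section 6: energy delivery attempted, unless Doc. No. 346 says otherwise. Align the enrollment sentences in section 3, section 5.1 and the first paragraph of section 6.
3. Use that definition for the primary endpoint and for every adverse event and serious adverse event table.
4. List separately, outside the denominator and with the follow-up actually available, adverse events and serious adverse events in endoscopic screen failures and in any patient whose procedure was abandoned before meeting the ITT definition.

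The cost is SAP wording and one listing. Protocol 196, section 5.4, already has serious adverse events in screen failures recorded on eCRFs; check that Doc. No. 346 does the same and also covers non-serious events.

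There is one small downside. Under the energy-attempted rule, a procedure-related serious event after catheter insertion but before any energy delivery appears in the listing and not in the primary proportion. The report should say so.
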